### 6.5.2 Whole Transcriptome RNA-Sequencing

In order to determine if and how adoptively transferred Tregs influence diseased tissue (i.e., skin), APG01 will perform whole transcriptome RNA-sequencing of skin biopsy samples taken from lesional skin before and after Treg adoptive transfer. This will allow for a comprehensive assessment of how adoptively transferred Tregs influence gene expression in skin, with a specific focus on pathways known to be important in the pathogenesis of pemphigus. As proof of concept, UCSF has recently performed RNA-sequencing on Tregs and Teff cells isolated from normal human skin. These populations were purified from relatively small samples of skin harvested from normal healthy volunteers (Figure 14A). Initial pathway analyses in Tregs compared to Teff cells have revealed IL-27-mediated signaling to be significantly increased and the IL-23 pathway to be significantly decreased in Tregs (Figure 14B). In a similar fashion, APG01 will comprehensively compare lesional skin pre-and post-Treg transfer to elucidate the major pathways that Tregs influence in skin.

**Figure 14, Whole transcriptome RNA-sequencing of Tregs and Teff cells isolated from normal human skin**

(A) Tregs and mTeff cells were sorted from normal skin using expression of CD25 and CD27. RNA was isolated from purified cell fractions (from 3 different healthy volunteers) and subjected to whole transcriptome RNA-sequencing. Scatter plot shows grouped Treg vs. Teff cell comparisons. (B) Ingenuity® Pathway Analyses of the IL-23 and IL-27 pathways showing genes increased (arrows) and inhibited (line ends) identified by RNA-seq to have greater than 2-fold changes between mTregs and

*mTeff cells with log p-values < 0.05. Genes in the IL-27 pathway were significantly activated in mTregs (activation Z-score of +2.4; p-value  $5.4 \times 10^{-4}$ ) and genes in the IL-23 pathway were shown to be significantly inhibited in mTregs (inhibition Z-score of -2.4; p-value  $3.0 \times 10^{-7}$ ).*

### 6.5.3 Functional Immunophenotyping of Skin and Blood

Cryopreserved PBMCs and single cell suspensions from fresh skin biopsies will be analyzed using multiparameter flow cytometry to assess changes in specific immune subsets following administration of expanded Tregs. The functionality of lymphocyte populations in blood and skin will be analyzed, specifically focusing on the cellular composition of the inflammatory infiltrate, T cell activation and intracellular cytokine expression profiles. T Helper Cell ( $T_H$ ) subset differentiation ( $T_{H1}$ ,  $T_{H2}$ , and  $T_{H17}$ ) and cytokine expression from Teffs and Tregs will be compared between blood and skin. Analyses will focus on Treg activation markers and proteins known to be involved in Treg function, including but not limited to: CD25, CD127, CTLA-4, GARP, CD39, Ki67, and CD27.

### 6.5.4 Treg Suppression Assays

Frozen PBMCs will be thawed and Tregs will be isolated by flow-based sorting using CD4, CD25 and CD127 (and in some cases CD45RA and CD45RO) antibodies. Tregs will be assayed for their ability to suppress polyclonal T cell proliferation using either carboxyfluorescein diacetate succinimidyl ester (CFSE) or  $^3$ [H]-thymidine in standard mixed suppression assays.

### 6.5.5 Autoantibody Analysis

Autoantibody titers, including Anti-Dsg1 and 3, will be assessed.

### 6.5.6 Lymphocyte Subset Analysis

Lymphocyte subsets include, but are not limited to (CD3 [T] cells, CD4 [helper] T cells, CD8 [cytotoxic] T cells, CD4+Foxp3+ Tregs, CD19 [B] cells, CD16 and CD56 Natural Killer [NK] cells).

### 6.5.7 Serum Cytokine Analysis

Collected serum will be stored for the measurement of cytokines. Serum will be assessed for pro-inflammatory cytokines (e.g., PDGF, IL-1 $\beta$ , IL-6, IL-12, TNF $\alpha$ ) and anti-inflammatory cytokines (e.g., TGF- $\beta$ , IL-10) by enzyme-linked immunosorbent assay (ELISA) and/or Luminex® bead assay to determine the effect of Treg treatment.

### 6.5.8 Treg Epigenetic Analysis

DNA purified from whole blood will be used to measure the frequency of Tregs in peripheral blood by means of epigenetic analysis. Analysis will be performed using the methylation-sensitive quantitative PCR (qPCR) method developed by Epiontis (Berlin, Germany) [68, 69]. This assay targets the demethylated state of the TSDR of the FOXP3 gene – a highly specific marker of Tregs. The proportion of CD4+CD25+CD127 cells as determined by flow cytometry strongly correlates with the proportion of demethylation of FOXP3 TSDR as

measured by qPCR. The proportion of demethylated FOXP3 will be normalized to proportion of demethylated CD3 DNA. The FOXP3 to CD3 ratio as determined by epigenetic analysis of methylation state strongly correlates with the ratio of Tregs to CD3+ cells as measured by flow cytometry [70].

### 6.5.9 Antigen Specific Studies

Because the antigenic targets in pemphigus are well defined, mechanistic studies will include attempts at quantifying T cell responses to the pemphigus autoantigens, Dsg1 & Dsg3, before and after PolyTreg therapy. These will include, but are not limited to, quantification of Dsg1- and/or Dsg3-specific T cells in peripheral blood and skin using MHC class II tetramers. In addition, we will determine the magnitude of antigen-specific T cell responses in peripheral blood before and after PolyTreg therapy by performing autologous mixed lymphocyte reactions with increasing concentrations of exogenous Dsg1 and/or Dsg3 peptides. Together, these studies will provide critical information regarding the number of antigen-specific pathogenic T cells and the functionality of these cells before and after PolyTreg therapy.

## 6.6 Unscheduled Visits

If disease activity increases or other concerns arise between regularly scheduled visits, subjects should be instructed to contact study personnel to determine whether an “unscheduled” visit should occur. The following evaluations will be performed at each unscheduled visit:

- Adverse Event Assessment
- Concomitant medication assessment
- Physical Examination
- Other evaluations may be performed at the investigator’s discretion

If the unscheduled visit is due to an increase in Pemphigus disease activity, these additional evaluations should also be performed:

- PDAI
- Desmoglein 1/3 autoantibodies by ELISA
- Skindex-29 (QOL)
- Physician’s Global Assessment (PhGA)
- Patient’s Global Assessment (PGA)
- Hematology Panel
- Chemistry Panel
- Digital Photography (optional)
- Lymphocyte subsets (optional)
- Mechanistic Blood Draw (optional)

Table 6.1, Schedule of Events (2 pages)																					
Visit Name	Screening E	Wk -2	Base-line	Day 1	Day 2	Day 3	Wk 1	Wk 2	Wk 3	Wk 5	Wk 8	Wk 12	Wk 14	Wk 26	Wk 39	Wk 52	Wk 78	Wk 104	Wk 130	Wk 156	Un-scheduled
Visit Window (days)	-49 to -42	-16 to -14	0	0	0	0	±3	±3	±3	±7	±7	±7	±7	±28	±28	±28	±28	±28	±28	±28	
Clinical Draw (ml) G	41	0	20.5	0	0	0	14	14	0	0	18	18	0	18	12	12	12	12	12	12	12
Study Product (ml)	0	400	0	0	0	0	0	0	0	0	0	0	0	0	0	0	0	0	0	0	0
Mechanistic Draw (ml)	0	0	35	0	0	0	30	35	0	0	30	35	0	35	0	35	0	0	0	0	35
Visit Draw Total (ml)	41	400	55.5	0	0	0	44	49	0	0	48	53	0	53	12	47	12	12	12	12	47
General Assessments (Section 6.1)																					
Informed consent	X																				
Demographics	X																				
Medical History	X																				
Physical Examination	X	X	X				X	X			X	X		X	X	X	X	X	X	X	X
Vital Signs	X	X	X	X			X	X			X	X		X	X	X	X	X	X	X	X
Medications Assessment	X		X				X	X			X	X		X	X	X	X	X	X	X	X
AE Assessment		X	X	X			X	X			X	X		X	X	X	X	X	X	X	X
AE Assessment by Phone					X	X			X	X			X								
Laboratory Assessments (Section 6.2)																					
Chest X-ray	X																				
Serum pregnancy test	X																				
Stat urine pregnancy test F		X	X D																		
Urine pregnancy test											X	X									
Hematology	X		X D				X	X			X	X		X	X	X	X	X	X	X	X
Chemistry	X		X D								X	X		X	X	X	X	X	X	X	X
Infectious Disease testing	X B																				
EBV & CMV IgG	X B																				
EBV & CMV Viral Load	X B						X	X			X	X		X							
TB Testing (PPD or QuantiFERON®-TB Gold In-Tube Test)	X B																				
Urinalysis with microscopic analysis	X															X					
Treg absolute count in peripheral blood	X																				
Disease Specific Assessments (Section 6.3)																					
Skin Biopsy for histopathology A	X A																				
PDAI	X		X				X	X			X	X		X	X	X	X	X	X	X	X

Table 6.1, Schedule of Events (2 pages)																					
Visit Name	Screening E	Wk -2	Base-line	Day 1	Day 2	Day 3	Wk 1	Wk 2	Wk 3	Wk 5	Wk 8	Wk 12	Wk 14	Wk 26	Wk 39	Wk 52	Wk 78	Wk 104	Wk 130	Wk 156	Un-sched-uled
Visit Window (days)	-49 to -42	-16 to -14	0	0	0	0	±3	±3	±3	±7	±7	±7	±7	±28	±28	±28	±28	±28	±28	±28	
Desmoglein 1/3 by ELISA	X		X				X	X			X	X		X	X	X	X	X	X	X	X
Skindex-29 (QoL)	X		X				X	X			X	X		X	X	X	X	X	X	X	X
Physician’s Global Assessment (PhGA)	X		X				X	X			X	X		X	X	X	X	X	X	X	X
Patient’s Global Assessment (PGA)	X		X				X	X			X	X		X	X	X	X	X	X	X	X
Digital photography	X		X				X	X			X	X		X	X	X	X	X	X	X	X C
Study Procedures																					
Blood Donation		X																			
PolyTreg Infusion			X																		
Mechanistic Assessments																					
Skin Biopsies			X				X					X									X C
Lymphocyte subsets			X					X				X		X		X					X C
Mechanistic Studies			X				X	X			X	X		X		X					X C

- A. Skin biopsy for histopathology at screening is required only if historic information does not satisfy Inclusion Criterion #3 (see Section 4.1, Inclusion Criteria).
- B. If a subject is rescreened within 3 months and there is no clinical indication to warrant a repeat test, previously negative EBV & CMV IgG, TB, and infectious disease tests do not need to be repeated.
- C. At the Un-scheduled Visit, the digital photography, skin biopsies, lymphocyte subsets, and mechanistic studies are optional.
- D. On the day of the scheduled infusion (Baseline Visit), blood chemistries, a complete blood count (CBC) with differential blood count, and a pregnancy test (for women of childbearing potential) will be obtained and reviewed locally prior to infusion of the PolyTregs.
- E. Screening Labs should be drawn within the window that complies with overall blood volume limitations per NIH guidance of no more than 550 cc in an 8-week period.
- F. Stat Pregnancy Test may be a urine or Point of Care (POC) test.
- G. The Clinical Draw blood volumes are approximate volumes that may vary across sites based on collection materials available.

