#### 5.6.1.3 Epstein-Barr Virus

Assessment for the presence of EBV genomes will be carried out according to the schedule outlined in Table 6.1, *Schedule of Events*. Management will depend on the presence or absence of symptoms and on the viral load.

For those with no or NCI-CTCAE Grade 1 or 2 symptoms judged at least possibly related to EBV reactivation:

- If EBV viral load is undetectable, study proceeds as per Table 6.1, *Schedule of Events*
- If EBV viral load is detectable and  $< 2000$  DNA copies per  $10^6$  PBMCs monitoring of EBV viral load may be increased as determined clinically necessary by the investigator
- If EBV viral load is  $\geq 2000$  DNA copies per  $10^6$  PBMCs monitoring of EBV viral load will be increased

For those with NCI-CTCAE Grade 3 or higher symptoms judged at least possibly related to EBV reactivation:

- If EBV viral load is undetectable, monitoring of EBV viral load will be increased as determined clinically necessary by the investigator
- If EBV viral load is detectable, monitoring of EBV viral load will be increased and appropriate treatment will be considered as determined clinically necessary by the investigator

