**APG01 PRE-INFUSION REQUIRED CHECKLIST**

Complete this form in preparation for the PolyTreg Infusion for all subjects who have a Baseline (Day 0) visit.  
Please note that all steps listed here must be completed before the start of the infusion.

Subject ID #: \_\_\_\_\_

Baseline Mechanistic Assessments: To be obtained after eligibility has been confirmed above Answer to each item must be Yes or N/A as applicable to proceed with the PolyTreg infusion.	Yes	No	N/A
10. Three skin biopsies were obtained and processed per Protocol Section 5.5.5 and MOP Section XX .			
11. Lymphocyte subsets were drawn (3mL in lavender top EDTA tube).			
12. Mechanistic specimens were drawn (20mL in two green top sodium heparin tubes).			
Certificate of Analysis/Chain of Custody Documentation			
13. Upon receipt of the subject's Treg product for infusion from the HICTF, the Interim Certificate of Analysis and the product's Chain of Custody have been reviewed and signed.			
Comments:  
SAMPLE
			

Signature/Initials: \_\_\_\_\_ Date: \_\_\_/\_\_\_/\_\_\_

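### Donation through Week 2 takes 548.5 ml of the 550 cc eight-week blood limit, so the 12 ml asked for at an early flare visit exceeds it, and footnote E, which governs only Screening timing, cannot prevent that

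*Combined protocol and SAP*

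**What the plan says.** Table 6.1, Schedule of Events, gives a blood volume for each visit. The totals from Screening to Week 12 read "Visit Draw Total (ml) 41 400 55.5 0 0 0 44 49 0 0 48 53", and the windows read "Visit Window (days) -49 to -42 -16 to -14 0 0 0 0 ±3 ±3 ±3 ±7 ±7". Footnote E adds the limit, which applies to an 8-week period: "Screening Labs should be drawn within the window that complies with overall blood volume limitations per NIH guidance of no more than 550 cc". Footnote G says that the clinical volumes are approximate and may differ by site.

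Section 6.6 covers unscheduled visits: "If the unscheduled visit is due to an increase in Pemphigus disease activity, these additional evaluations should also be performed". The list that follows includes the desmoglein ELISA, hematology and chemistry, none of them marked optional. It also includes an item that is: "Mechanistic Blood Draw (optional". The Unscheduled column of Table 6.1 puts the clinical draw at 12 ml and the mechanistic draw at 35 ml.

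The pre-infusion checklist in Section 15.6 gives a different Day 0 research volume from the table. Item 12 reads "Mechanistic specimens were drawn (20mL in two green top sodium heparin tubes", and item 11 adds 3 ml for lymphocyte subsets, which makes 23 ml. Table 6.1 has 35 ml of mechanistic blood at Baseline.

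**The concern.** The limit and the schedule sit in the same table, but the only control on the limit is the choice of Screening date. Moving Screening earlier makes no room for blood drawn after the donation. If the scheduled draws alone nearly fill the allowance, any further blood in that period exceeds it, and the protocol gives no rule for omitting, reducing or offsetting a draw.

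The subjects affected would be those whose disease worsens in the weeks around infusion. They will have given about 400 ml, and Section 4.2 lets them enter with a hemoglobin as low as 10 g/dl. A site seeing such a subject has to exceed the limit or decide for itself which blood to leave out.

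**Working it through.** **Inputs (Table 6.1).** The clinical row reads "Clinical Draw (ml) G 41 0 20.5 0 0 0 14 14 0 0 18 18 0 18 12 12 12 12 12 12 12". Adding study product and mechanistic blood reproduces the printed totals:

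| Visit | Day | Clinical + product + mechanistic | Total (ml) |
|---|---|---|---|
| Screening | -49 to -42 | 41 + 0 + 0 | 41 |
| Week -2 (donation) | -16 to -14 | 0 + 400 + 0 | 400 |
| Baseline | 0 | 20.5 + 0 + 35 | 55.5 |
| Week 1 | 4 to 10 | 14 + 0 + 30 | 44 |
| Week 2 | 11 to 17 | 14 + 0 + 35 | 49 |
| Week 8 | 49 to 63 | 18 + 0 + 30 | 48 |
| Unscheduled | any | 12 + 0 + 35 | 47 |

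All 21 columns of the table add up.

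**Scheduled blood, donation to Week 2.** The span is at least 11 - (-14) = 25 days and at most 17 - (-16) = 33 days, so the four draws always share one 8-week period: 400 + 55.5 + 44 + 49 = 548.5 ml, leaving 550 - 548.5 = 1.5 ml. Week 8 falls at least 49 - (-14) = 63 days after donation and never joins them.

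**One flare visit in that period.**
- Non-optional bloods: 548.5 + 12 = 560.5 ml, which is 10.5 ml over.
- With the optional mechanistic draw: 548.5 + 47 = 595.5 ml.
- End of the period: counting 56 calendar days including the donation day, Day -16 + 55 = 39 to Day -14 + 55 = 41. Counting a 56-day difference, Day 40 to 42.
- If infusion is withheld, there are no Week 1 or Week 2 draws: 400 + 55.5 + 12 = 467.5 ml, or 467.5 + 41 = 508.5 ml with Screening. Both are within the limit.

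**Screening and Week 2 in one period.** 548.5 + 41 = 589.5 ml, which is 39.5 ml over. There are 8 permitted Screening days and 7 permitted Week 2 days, so 56 pairs.
- Counting 56 calendar days inclusively, 6 pairs share a period: Day -44 with Day 11, Day -43 with Days 11 and 12, and Day -42 with Days 11 to 13.
- Counting a 56-day difference, 10 pairs do. This brings in Day -45 with Day 11 and the nominal pair Day -42 with Day 14.
- Screening on Day -46 or earlier never overlaps Week 2 under either count. Screening through Week 1 alone is 41 + 400 + 55.5 + 44 = 540.5 ml, within the limit.

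**Sensitivity to the Day 0 volume.** With 23 ml in place of 35 ml at Baseline, the scheduled total is 548.5 - 12 = 536.5 ml. One flare visit (12 ml) gives 548.5 ml, within the limit. Screening overlap gives 536.5 + 41 = 577.5 ml, still over.

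**The case against.** **The Screening route is already addressed.** Footnote E tells sites to time Screening so as to comply, and a site that picks an early day does. This stands in part. The 6 (or 10) of 56 pairs might be read as a breach rate, but they are only a count of calendar combinations that the footnote asks sites to avoid. What remains is that the printed window permits those days, and a site cannot know at Screening whether Week 2 will be early.

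**The flare route is conditional.** A reader might infer that any flare visit in the period exceeds the limit. The documents do not support that. A PDAI above 12 on the infusion day withholds infusion (Section 5.3.4), and the total then stays below 550 ml. A flare around Days 4 to 17 may be seen at a scheduled visit. The 12 ml overshoots only if 35 ml is the true Day 0 volume. The checklist is weak evidence for 23 ml, because it is stamped as a sample and has an unfilled cross-reference. The 595.5 ml figure needs a draw that a site may omit.

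**The volumes are approximate.** Footnote G says so for clinical blood, Section 6.4 calls the donation approximate, and Section 5.1.1 calls 400 ml a target. An overshoot of 10.5 ml is under 2% of the limit (10.5/550 = 1.9%), and a smaller donation would remove it. This stands, but the variation can go either way, and a 1.5 ml margin absorbs none of it.

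**Extra EBV testing.** Section 5.6.1.3 says that in some subjects "monitoring of EBV viral load will be increased". It gives no volume or date. The difference between Week 26 and Week 39 clinical blood, 18 - 12 = 6 ml, suggests a figure for EBV and CMV together, which would give 554.5 ml. That is an inference, and the point does not rest on it.

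**The harm.** It is tempting to say that flares cluster just after infusion, or that sites must drop safety bloods. The documents show neither. Weeks 1 and 2 each include 30 to 35 ml of research blood that could be reduced instead.

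**Conclusion.** The limit and the schedule conflict. The scheduled visits alone comply, at 548.5 ml. In an infused subject who attends Weeks 1 and 2, one flare visit between donation and about Day 39 to 42 takes the total to 560.5 ml on non-optional bloods, and footnote E has no means of preventing it. This assumes the table's volumes, including 35 ml of mechanistic blood at Day 0.

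The Screening overlap (589.5 ml) is a secondary gap: avoidable under footnote E, but permitted by the printed window on Days -44 to -42, or from Day -45 if a 56-day difference counts.

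The matter concerns study conduct and subject burden. It changes no endpoint or analysis. It is worth correcting because the protocol sets the limit itself and the correction is cheap.

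**What to change.** 1. Extend footnote E to every draw until 8 weeks after the donation, and state how the 8 weeks are counted.
2. In that period, exclude the optional 35 ml mechanistic draw at unscheduled visits.
3. Reserve room in advance by cutting Baseline-to-Week 2 research blood by at least 10.5 ml in total. Offsetting against the next mechanistic draw does not work for a flare after Week 2, because Week 8 lies outside the period. First reconcile the Day 0 volume between Table 6.1 (35 ml) and the checklist (23 ml). If 23 ml is enough for the assays, the scheduled total is 536.5 ml and one flare visit brings it to 548.5 ml. A cut at Baseline is preferable to one at Week 2 alone, because Screening through Week 1 plus a flare visit is 540.5 + 12 = 552.5 ml, which a Week 2 cut would not reduce.
4. Close the Screening window at Day -46, which is safe against an early Week 2 under either day count.

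The cost is table and footnote edits, slightly less early research blood, the loss of one optional sample, and a Screening window 4 days shorter (Day -49 to -46 in place of Day -49 to -42).

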## 7 SAFETY MONITORING AND REPORTING

### 7.1 Overview

This section defines the types of safety data that will be collected under this protocol and outlines the procedures for appropriately collecting, grading, recording, and reporting that data. AEs that are classified as serious according to the definition of health authorities must be reported promptly (per Section 7.5, *Reporting of Adverse Events and Serious Adverse Events to the Sponsor: DAIT/NIAID*) and appropriately to the investigational new drug application (IND) sponsor (DAIT, NIAID), principal investigators in the trial, IRBs, and health authorities. Information in this section complies with *International Conference on Harmonization (ICH) Guideline E2A: Clinical Safety Data Management: Definitions and Standards for Expedited Reporting*, *ICH Guideline E-6: Guideline for Good Clinical Practice*, and applies the standards set forth in the NCI-CTCAE, *Version 4.0*: [https://ctep.cancer.gov/protocolDevelopment/electronic\\_applications/ctc.htm#ctc\\_40](https://ctep.cancer.gov/protocolDevelopment/electronic_applications/ctc.htm#ctc_40)

### 7.2 Definitions

#### 7.2.1 Adverse Event (or Adverse Experience)

Any untoward or unfavorable medical occurrence in a human subject, including any abnormal sign, symptom, or disease, temporally associated with the subject's participation in the research, whether or not considered related to the subject's participation in the research (modified from the definition of AEs in the 1996 ICH E-6 Guidelines for Good Clinical Practice)." [From Office for Human Research Protections (OHRP) "Guidance on Reviewing and Reporting Unanticipated Problems Involving Risks to Subjects or Others and Adverse Events (1/15/07)" <http://www.hhs.gov/ohrp/policy/advevntguid.html>]

#### 7.2.2 Adverse Reaction and Suspected Adverse Reaction

An adverse reaction means any AE caused by a drug. Adverse reactions are a subset of all suspected adverse reactions for which there is reason to conclude that the drug caused the event.

Suspected adverse reaction (SAR) means any AE for which there is a reasonable possibility that the drug caused the AE. For the purposes of safety reporting, 'reasonable possibility' means there is evidence to suggest a causal relationship between the drug and the AE. A SAR implies a lesser degree of certainty about causality than adverse reaction, which means any AE caused by a drug (21 CFR 312.32(a)).

#### 7.2.3 "Expected" versus "Unexpected" Suspected Adverse Reaction

A SAR is considered "expected" when it is listed in the investigator brochure, the general investigational plan, or the Protocol. A SAR is considered "unexpected" when its nature (specificity), severity, or rate of occurrence is not consistent with applicable product information as described in the safety information provided in the investigator brochure, the general investigational plan, or the protocol (21 CFR 312.32(a) and ICH E2A). A serious unexpected suspected adverse drug reaction is referred to as a SUSAR. For this study,

expectedness will be determined by product information provided in the investigator brochure (IB).

